9.3 Clinical Laboratory Data

For each quantitative laboratory parameter, descriptive statistics of actual measurements and changes from baseline at each time point and the final assessment (Week 14 LOCF) will be calculated.

For each quantitative laboratory parameter, actual measurements will be classified as "lower than the lower limit of the reference range," "within the reference range," and "higher than the upper limit of the reference range" using the reference range specified by the central laboratory, and a shift table from baseline will be produced.

For each qualitative laboratory parameter, a shift table from baseline will be produced.

Numbers and proportions of subjects with laboratory test values not meeting the criteria for potentially clinically significant laboratory test values (Appendix 2) at baseline and meeting the criteria after treatment will be determined. A listing of these subjects will be provided.

Numbers and proportions of subjects with postdose values of alanine aminotransferase (ALT), aspartate aminotransferase (AST), and total bilirubin (TBL) meeting Hy's Law criteria (ALT or $AST \geq 3 \times$ the upper limit of normal [ULN] and $TBL \geq 2 \times$ ULN) will be determined. A listing of these subjects will be provided.

Numbers and proportions of subjects with a prolactin value not meeting the criteria of $> 1 \times$ ULN, $> 2 \times$ ULN, or $> 3 \times$ ULN at baseline and meeting the criteria after treatment will be determined by sex. A listing of these subjects will be provided.

Numbers and proportions of subjects with postdose values of fasting low-density lipoprotein (LDL) cholesterol, high-density lipoprotein (HDL) cholesterol, triglyceride, and blood glucose meeting the criteria for changes in glucose and lipid metabolism-related parameters (Table 9.3-1) will be determined by baseline value. A listing of these subjects will be provided.

Table 9.3-1 Changes in Glucose and Lipid Metabolism-related Parameters		
LAB PARAMETER	BASELINE	ANYTIME POST BASELINE
Cholesterol, Fasting (mg/dL)	Normal <200 Borderline 200-<240 Normal/Borderline <240 Normal <200 Any Value	High >=240 High >=240 High >=240 Borderline/High >=200 Increased >=40
LDL Cholesterol, Fasting (mg/dL)	Normal <100 Borderline 100-<160 Normal/Borderline <160 Normal <100 Any Value	High >=160 High >=160 High >=160 Borderline/High >=100 Increased >=30
HDL Cholesterol, Fasting (mg/dL)	Normal >=40 Any Value	Low <40 Decreased >=20
Triglycerides, Fasting (mg/dL)	Normal <150 Normal <150 Borderline 150-<200 Normal/Borderline <200 Normal/Borderline <200 Normal <150 Normal/Borderline/high <500 Any Value	High 200-<500 Very High >=500 High 200-<500 High 200-<500 Very High >=500 Borderline/High/Very High >=150 Very High >=500 Increased >=50
Glucose Fasting, Serum (mg/dL)	Normal <100 Impaired 100-<126 Normal/Impaired <126 Any Value	High >=126 High >=126 High >=126 Increased >=10

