11	Patients whose laboratory test results at evaluation at Week 10 of Trial 331-102-00088 meet either of the following criteria for poor blood glucose control (assessed on the basis of the results from the central or local laboratory): 
 Glycosylated hemoglobin (HbA1c) of $\geq 8.0\%$ according to the global standard value (NGSP value) Fasting blood glucose level of $\geq 126 \text{ mg/dL}$ or nonfasting blood glucose level of $\geq 200 \text{ mg/dL}$
12	Patients who had neuroleptic malignant syndrome, tardive dyskinesia, paralytic ileus, or rhabdomyolysis during Trial 331-102-00088.
13	Patients who had convulsive disorders (eg, epilepsy) in Trial 331-102-00088, not including patients with febrile seizure, post-traumatic seizure, or alcohol withdrawal seizure.
14	Patients who are unable to take oral medication due to severe dysphagia.

Table 3.4.3-1 Exclusion Criteria	
15	Patients whose Sheehan Suicidality Tracking Scale (S-STS) score in Trial 331-102-00088 meets any of the following criteria, or who are judged by the investigator or subinvestigator to be at high risk of suicide: 
 • Patients with a score of 3 or 4 on any of S-STS Questions 2, 3, 4, 5, 6, or 11 • Patients with a score of 2 or more on any of S-STS Questions 1a, 7, 8, 9, 10, or 12
16	Patients whose body weight at evaluation at Week 10 of Trial 331-102-00088 was < 30 kg.
17	Patients whose body weight had fallen by ≥ 7% at Week 10 from baseline in Trial 331-102-00088.
18	Patients who were confirmed to meet the following contraindications in the package insert of REXULTI® during Trial 331-102-00088: 
 • Patients in a coma • Patients under the strong influence of central nervous system depressants, including barbiturate analogs/anesthetics • Patients receiving adrenaline • Patients with a history of hypersensitivity to the components of REXULTI®
19	Patients who are bedridden and require assistance for excretion, eating, and changing clothes
20	Women who had a positive pregnancy test result at Week 10 of Trial 331-102-00088 (women of childbearing potential only)

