3.8.2.2 Clinical Laboratory Assessments

In this trial, the clinical laboratory tests shown in Table 3.8.2.2-1 will be conducted by central analysis. Blood and urine samples will be collected from each subject, and the date and time of blood sampling, the date of urine sampling, and the verification of whether blood sampling was performed when the subject was in a fasted state (having fasted for at least 8 hours) will be recorded in the source documents and the CRF. Subject eligibility will be verified using the clinical laboratory test values determined at the central or local laboratory. If laboratory test values determined at the local laboratory are used for verification of subject eligibility, it must first be verified that quality control has been performed. If any of the test results provided by the central laboratory at a later date falls under the exclusion criteria, the subject will be withdrawn from the trial. For appropriate procedures for the collection, handling, and shipment of samples analyzed at the central laboratory, the separately prepared procedures should be followed. The total amount of blood to be collected for clinical laboratory tests during the trial period will be described in the ICF and explanatory materials.

The central laboratory will report the results of tests to the investigator or subinvestigator. The investigator or subinvestigator will confirm the results of tests and date and sign the clinical laboratory test report to make it an official document. The results of laboratory tests, which will be reported directly from the central laboratory to the sponsor as an electronic file, do not need to be recorded in the source documents or the CRF.

Table 3.8.2.2-1 Clinical Laboratory Assessments	
Hematology:	Serum chemistry:
Red blood cell count	ALT
White blood cell count	AST
Differential count of white blood cells (neutrophils, eosinophils, basophils, monocytes, and lymphocytes)	Alkaline phosphatase (ALP)
Platelet count	Lactic dehydrogenase (LDH)
Hemoglobin	Gamma-glutamyl transpeptidase (γ -GTP)
Hematocrit	Total protein
Prothrombin time (PT)	Total bilirubin
PT (international normalized ratio [INR])	Albumin
Activated partial thromboplastin time (APTT)	Cholesterol (total cholesterol, low-density lipoprotein [LDL] cholesterol, and high-density lipoprotein [HDL] cholesterol)
Urinalysis:	Triglycerides
pH	Blood urea nitrogen (BUN)
Protein	Creatinine
Glucose	Uric acid
Occult blood	CPK

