Urobilinogen	Blood electrolytes (Na, K, Cl, Mg, Ca, P,)
Specific gravity	Blood glucose (fasting or nonfasting)
Ketone body	HbA1c (NGSP value)
	Endocrinology:
	Serum prolactin
	Insulin

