Appendix 2 **Criteria for Identifying Laboratory Values of Potential Clinical Relevance**

Laboratory Tests	Criteria
Chemistry	
AST (SGOT)	$\geq 3 \times$ upper limit of normal (ULN)
ALT (SGPT)	$\geq 3 \times$ ULN
Alkaline phosphatase	$\geq 3 \times$ ULN
LDH	$\geq 3 \times$ ULN
BUN	≥ 30 mg/dL
Creatinine	≥ 2.0 mg/dL
Uric Acid	
Men	≥ 10.5 mg/dL
Women	≥ 8.5 mg/dL
Bilirubin (total)	≥ 2.0 mg/dL
CPK	$\geq 3 \times$ ULN
Endocrinology	
Prolactin	$>$ ULN
Hematology	
Hematocrit	
Men	$\leq 37\%$ and decrease of ≥ 3 percentage points from Baseline
Women	$\leq 32\%$ and decrease of ≥ 3 percentage points from Baseline
Hemoglobin	
Men	≤ 11.5 g/dL
Women	≤ 9.5 g/dL
White blood count	$\leq 2,800/\text{mm}^3$ or $\geq 16,000/\text{mm}^3$
Eosinophils	$\geq 10\%$
Neutrophils	$\leq 15\%$
Absolute neutrophil count	$\leq 1,000/\text{mm}^3$
Platelet count	$\leq 75,000/\text{mm}^3$ or $\geq 700,000/\text{mm}^3$
Urinalysis	
Protein	Increase of ≥ 2 units
Glucose	Increase of ≥ 2 units
Additional Criteria	
Chloride	≤ 90 mEq/L or ≥ 118 mEq/L
Potassium	≤ 2.5 mEq/L or ≥ 6.5 mEq/L
Sodium	≤ 126 mEq/L or ≥ 156 mEq/L
Calcium	≤ 8.2 mg/dL or ≥ 12 mg/dL
Glucose	
Fasting	≥ 100 mg/dL
Non-Fasting	≥ 200 mg/dL
Total Cholesterol, Fasting	≥ 240 mg/dL
LDL Cholesterol, Fasting	≥ 160 mg/dL
HDL Cholesterol, Fasting	
Men	< 40 mg/dL
Women	< 50 mg/dL
Triglycerides, Fasting	≥ 150 mg/dL

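### SAP 9.3 gives no fasting rule for laboratory mean changes, LOCF or shifts, so glucose, triglyceride and insulin changes can compare fed with fasted samples

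*SAP*

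**What the plan says.** **Collection.** Protocol 3.8.2.2 states that "verification of whether blood sampling was performed when the subject was in a fasted state (having fasted for at least 8 hours) will be recorded"; the entry is made both on the CRF and at source. Neither document requires a fasted sample. Table 3.8.2.2-1 lists glucose as "Blood glucose (fasting or nonfasting", and lists triglycerides and insulin as single parameters. Baseline laboratory values are the parent trial's Week 10 results (protocol Table 3.8-1).

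**Continuous summaries and shifts.** SAP 9.3 plans "For each quantitative laboratory parameter, descriptive statistics of actual measurements and changes from baseline at each time point" and at Week 14 LOCF, plus a below/within/above reference-range shift table for each such parameter. Fasting state is not mentioned. SAP 3.4 takes the last value in a visit window, and SAP 5.3 carries forward the last post-dose value; neither looks at fasting state.

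**Threshold counts.** For Table 9.3-1, SAP 9.3 plans "Numbers and proportions of subjects with postdose values of fasting low-density lipoprotein (LDL) cholesterol" and the other lipid and glucose rows, also fasting, tabulated by baseline value. In Appendix 2 the lipid rows are fasting (for example "Total Cholesterol, Fasting"). Glucose there has two limits: fasting at or above 100 mg/dL and non-fasting at or above 200 mg/dL.

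**Entry.** Exclusion criterion 11 in protocol 3.4.3, the "criteria for poor blood glucose control", also uses different glucose limits by state: 126 mg/dL fasting and 200 mg/dL non-fasting.

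**The concern.** The plan recognises that a fasting and a non-fasting glucose value are not interchangeable: it uses separate limits for them at entry and in Appendix 2, and restricts Table 9.3-1 to fasting samples. That distinction is absent from the mean-change, LOCF and shift rules, which are the only planned summaries for insulin.

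A programmer who follows SAP 9.3 would take whatever sample falls in the window and subtract whatever baseline exists. If fasting state differs between the two, the change includes a meal effect. In a randomised comparison this would tend to affect both arms alike. Here all subjects receive brexpiprazole, so a drift in fasting practice between the parent trial's Week 10 visit and later visits would look like a drug effect or hide one. Glucose- and lipid-related events are adverse events of interest (SAP 9.2.1), and these tables are the objective evidence beside them.

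A smaller gap is that SAP 9.3 does not state who is in the denominator of the fasting-only proportions.

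**Working it through.** **Plan's own figure.** The target is 100 prior-brexpiprazole completers, and the parent allocation of 3:4:4 puts 7/11 on brexpiprazole. 100 ÷ (7/11) = 157.1, so 157 is reproduced. It is used below only as a base for counts.

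**Is pooling what the text says?** The SAP does not say that fed and fasted values are combined; this is inferred from the absence of a rule. The table list in SAP Appendix 4 supports the inference. Where a split is intended it is named: prolactin mean change and shifts are by gender (CT-10.1.4, CT-10.2.5). The serum chemistry tables (CT-10.1.1, CT-10.2.1) name no fasting split.

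**Effect on a mean change.** Let D be the fed-minus-fasted difference and Δ the change in the fasting share between baseline and a later visit. With no metabolic change, the pooled mean change moves by D × Δ in size. Neither quantity is in the documents, so both are assumed:

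- D = 10 mg/dL, Δ = 0.10: 1 mg/dL
- D = 20 mg/dL, Δ = 0.20: 4 mg/dL
- D = 40 mg/dL, Δ = 0.30: 12 mg/dL

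If the fasting share is stable (Δ = 0) the mean is not biased. Individual changes and shift classifications are still affected for every mismatched pair.

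**How often pairs mismatch, and the denominator.** Assume each sample is fasted with probability p, independently. Cell positions in protocol Table 3.8-1 suggest three post-baseline laboratory visits (the column headers are partly lost).

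- Mismatch with baseline at one visit: 2p(1−p).
- At least one fasting post-baseline value: 1−(1−p)³.
- Fasting baseline and at least one fasting post-baseline value, of 157: 157 × p × [1−(1−p)³].
- Understatement of a Table 9.3-1 proportion if the denominator is everyone with a fasting baseline: 1 ÷ [1−(1−p)³]. This denominator follows from tabulating by baseline value, since a subject without a fasting baseline belongs in no baseline row.

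| p | Mismatch at one visit | At least one fasting post-baseline value | Evaluable of 157 | Understatement factor |
|---|---|---|---|---|
| 0.2 | 0.32 | 0.488 | 15 | 2.0 |
| 0.3 | 0.42 | 0.657 | 31 | 1.5 |
| 0.5 | 0.50 | 0.875 | 69 | 1.14 |
| 0.8 | 0.32 | 0.992 | 125 | 1.01 |

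If the same subjects tend to fast each time, mismatch is rarer and the understatement smaller than shown.

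**The case against.** The strongest reply is that the SAP already separates the two states. Table 9.3-1 names fasting serum glucose as a parameter, Appendix 2 separates fasting from non-fasting glucose, and a rule written per parameter could be read as treating them separately. That reading is possible for glucose. It is harder for triglycerides and insulin, which the laboratory panel lists once each, and it does not say how a subject whose state changes is handled. Even if separate handling was intended, it needs to be written.

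A reader might also infer several stronger points that the documents do not support:

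- **That metabolic worsening is missed.** HbA1c is on the panel, does not depend on fasting, and as a quantitative parameter gets mean change, minimum and maximum, LOCF and a reference-range shift. Laboratory results are listed (LAB-1 to LAB-4), and a value judged medically relevant is an adverse event (protocol 5.1). HbA1c lacks only a threshold count.
- **That the HbA1c withdrawal limit of 8.0% is an on-treatment rule which the outcome tables fail to mirror.** Protocol 3.9.3.2 applies it only to parent-trial Week 10 results that arrive after dosing has started.
- **That all threshold and shift counts are fasting-only.** Appendix 2 counts non-fasting glucose at or above 200 mg/dL, and the reference-range shifts take samples of any state.
- **That fasting-only proportions are diluted up to tenfold.** That requires dividing by all 157 subjects (157 ÷ 15 is about 10 at p = 0.2), which does not fit a table tabulated by baseline value.

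**Conclusion.** The point holds for fasting-state matching. As written, SAP 9.3 permits fed-versus-fasted comparisons in the mean changes, LOCF changes and shifts of glucose, triglycerides and insulin, and an uncontrolled trial cannot separate the resulting meal effect from a drug effect. The metabolic signal is blurred rather than lost.

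The size cannot be determined from the documents. The 1 to 12 mg/dL range rests on assumed values of D and Δ. The mismatch shares of 0.32 to 0.50 rest on assumed p and on independence between visits.

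The denominator is a secondary matter of missing detail. The understatement factor runs from about 2.0 to 1.01 under the same assumptions and three post-baseline visits, and is minor once half or more of the samples are fasted. The HbA1c threshold is an optional improvement, not a defect.

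**What to change.** In SAP 9.3:

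1. For glucose, triglycerides and insulin, calculate change from baseline, LOCF change and reference-range shifts only between samples of the same recorded fasting state. Show fasting and non-fasting separately, each with the number of subjects contributing.
2. For Table 9.3-1 and the fasting rows of Appendix 2, state that the denominator is subjects with a fasting baseline and at least one fasting post-baseline value.
3. Optionally, add a categorical summary of HbA1c for reporting only. The sponsor should choose the cut-points: a single count at the 8.0% entry limit would not register a rise from 5.5% to 7.9%.

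The cost is SAP text and programming; no sampling or clinical rule changes. The fasting flag and HbA1c are already collected. For the baseline sample, drawn in the parent trial, the flag is assumed to be available, since exclusion criterion 11 needs it.

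The downside is smaller numbers. Under the independence assumption, and before any missing data, the matched subjects at one visit out of 157 would be 157 × p² fasting and 157 × (1−p)² non-fasting: about 6 and 100 at p = 0.2, 14 and 77 at p = 0.3, 39 and 39 at p = 0.5, and 100 and 6 at p = 0.8.

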9.4 Vital Sign Data

For each vital sign parameter (sitting position), descriptive statistics of actual measurements and changes from baseline at each time point and the final assessment (Week 14 LOCF) will be calculated.

Numbers and proportions of subjects with vital signs meeting the criteria for potentially clinically significant vital signs (Appendix 1) will be determined. A listing of these subjects will be provided.

9.5 Physical Examination Data

Physical examination data will be provided in a listing.

9.6 Electrocardiogram Data

For heart rate, PR interval, RR interval, QRS interval, QT interval, and QT corrected for heart rate (QTc), descriptive statistics of actual measurements and changes from baseline at each time point and the final assessment (Week 14 LOCF) will be calculated.

A shift table from baseline for normal/abnormal 12-lead electrocardiogram (ECG) (evaluated at the trial site) will be produced.

Numbers and proportions of subjects with actual measurements of QTc [QTcF, QTcB, QTcN = QT interval/(RR interval)^{0.37}] not meeting the criteria of > 450 msec, > 480 msec, or > 500 msec at baseline and meeting the criteria after treatment will be determined. Numbers and proportions of subjects with changes from baseline of > 30 msec and > 60 msec will be determined. Numbers and proportions of subjects with actual measurements of > 450 msec with a % change from baseline of > 10% will be determined.

Numbers and proportions of subjects with ECG results meeting the criteria for potentially clinically significant ECG data (Appendix 3) will be determined. A listing of these subjects will be provided.

9.7 Other Safety Data

9.7.1 Body Weight and BMI

For body weight and BMI, descriptive statistics of actual measurements and changes from baseline at each time point and the final assessment (Week 14 LOCF) will be calculated.

Numbers and proportions of subjects with results meeting the criteria for potentially clinically significant body weight gain or loss (Appendix 1) will be determined. Body weight data will also be analyzed by baseline BMI category (< 18.5, ≥ 18.5 to < 25, ≥ 25 to < 30, ≥ 30) in a similar manner. A listing of subjects with results meeting the criteria for potentially clinically significant body weight gain or loss (Appendix 1) will be provided.

9.7.2 DIEPSS, AIMS, and BARS

For DIEPSS total score (total of scores for items 1 through 8) and score for each DIEPSS item, AIMS total score (total of scores for items 1 through 7) and score for each of the 3 global judgment items (items 8 through 10), and BARS, descriptive statistics of actual measurements and changes from baseline at each time point and the last assessment time point (Week 14 LOCF) and the worst postdose measurement and its change from baseline will be calculated.

9.7.3 S-STS

For the score for each S-STS item (2 through 14), total score, suicidal ideation subscale score, and suicidal behavior subscale score, descriptive statistics of actual measurements

and changes from baseline at each time point and the final assessment (Week 14 LOCF) will be calculated.

10 Pharmacokinetic Analyses

Not applicable.

11 Pharmacodynamic Analyses

Not applicable.

12 Pharmacogenomic Analyses

Not applicable.

13 Analysis of Other Endpoints

Analysis of other endpoints will be performed using the safety analysis set. Baseline is defined as the last data obtained prior to initiation of IMP treatment.

- ADCS-ADL
- MMSE

For ADCS-ADL total score and MMSE total score, descriptive statistics of actual measurements and changes from baseline at each time point and the final assessment (Week 14 LOCF) will be calculated.

14 Interim Analysis

In this trial, safety will also be evaluated by the IDMC, when approximately 25%, 50%, and 75% of the target number of subjects in the preceding Trial 331-102-00088 have completed or discontinued the trial. Additional evaluation by the IDMC may be performed depending on the status of subject enrollment into the current trial (331-102-00184).

A statistical analysis plan for interim analysis is described in a separate interim analysis plan.

15 Changes in the Planned Analyses

[REDACTED]

The following changes were made to categorical analyses of QTc:

- Only subjects with postdose QTc meeting the criteria will be summarized, instead of summarization at all time points.
- Only subjects with QTc not meeting the criteria at baseline and meeting the criteria after baseline will be summarized.

16 References

Not applicable.

Appendix 1 **Criteria for Identifying Vital Signs and Weight of Potential Clinical Relevance**

Variable	Criterion Value ^a	Change Relative to Baseline ^a
Pulse Rate	> 120 bpm < 50 bpm	≥ 15 bpm increase ≥ 15 bpm decrease
Systolic Blood Pressure	> 180 mmHg < 90 mmHg	≥ 20 mmHg increase ≥ 20 mmHg decrease
Diastolic Blood Pressure	> 105 mmHg < 50 mmHg	≥ 15 mmHg increase ≥ 15 mmHg decrease
Weight	-	≥ 7% increase ≥ 7% decrease

^aIn order to be identified as potentially clinically relevant, an on-treatment value must meet the “Criterion Value” and also represent a change from the subject’s baseline value of at least the magnitude shown in the “Change Relative to Baseline” column.

Appendix 2 **Criteria for Identifying Laboratory Values of Potential Clinical Relevance**

Laboratory Tests	Criteria
Chemistry	
AST (SGOT)	$\geq 3 \times$ upper limit of normal (ULN)
ALT (SGPT)	$\geq 3 \times$ ULN
Alkaline phosphatase	$\geq 3 \times$ ULN
LDH	$\geq 3 \times$ ULN
BUN	≥ 30 mg/dL
Creatinine	≥ 2.0 mg/dL
Uric Acid	
Men	≥ 10.5 mg/dL
Women	≥ 8.5 mg/dL
Bilirubin (total)	≥ 2.0 mg/dL
CPK	$\geq 3 \times$ ULN
Endocrinology	
Prolactin	$>$ ULN
Hematology	
Hematocrit	
Men	$\leq 37\%$ and decrease of ≥ 3 percentage points from Baseline
Women	$\leq 32\%$ and decrease of ≥ 3 percentage points from Baseline
Hemoglobin	
Men	≤ 11.5 g/dL
Women	≤ 9.5 g/dL
White blood count	$\leq 2,800/\text{mm}^3$ or $\geq 16,000/\text{mm}^3$
Eosinophils	$\geq 10\%$
Neutrophils	$\leq 15\%$
Absolute neutrophil count	$\leq 1,000/\text{mm}^3$
Platelet count	$\leq 75,000/\text{mm}^3$ or $\geq 700,000/\text{mm}^3$
Urinalysis	
Protein	Increase of ≥ 2 units
Glucose	Increase of ≥ 2 units
Additional Criteria	
Chloride	≤ 90 mEq/L or ≥ 118 mEq/L
Potassium	≤ 2.5 mEq/L or ≥ 6.5 mEq/L
Sodium	≤ 126 mEq/L or ≥ 156 mEq/L
Calcium	≤ 8.2 mg/dL or ≥ 12 mg/dL
Glucose	
Fasting	≥ 100 mg/dL
Non-Fasting	≥ 200 mg/dL
Total Cholesterol, Fasting	≥ 240 mg/dL
LDL Cholesterol, Fasting	≥ 160 mg/dL
HDL Cholesterol, Fasting	
Men	< 40 mg/dL
Women	< 50 mg/dL
Triglycerides, Fasting	≥ 150 mg/dL

